16.4. VITAL SIGNS

The following Vital Signs measurements will be reported for this study:

- Supine Systolic Blood Pressure (mmHg)
- Supine Diastolic Blood Pressure (mmHg)
- Supine Pulse Rate (bpm)

The following summaries will be provided for vital signs data:

 Actual assessments at screening, baseline (pre-dose at each treatment period) and each post-dose time points, including end of study visit and overall (where overall is regardless of treatment period, day and timepoint to assess treatment group as a whole).

16.5. PHYSICAL EXAMINATION

The following summaries will be provided for the full physical examination data, covering major body systems (nose, throat, skin, thyroid gland, neurological system, respiratory system, cardiovascular system, abdomen [liver and spleen], lymph nodes and extremities):

- Incidence of abnormalities at screening
- Incidence of abnormalities at end of study
- Changes in abnormalities between screening and end of study

The following summaries will be provided for a brief physical examination to be also performed, on skin, respiratory system, cardiovascular system, and abdomen (liver and spleen):

• Incidence of abnormalities pre-dose on Day 1

Document: Z:\RPL554\UYA25849\Biostatistics\Documentation\SAP\Verona RPL554-CO-204 SAP v1.0

Author: [name] Version Number: 1.0

Version Date: [18OCT2018]

Template No.: CS_TP_BS016 Revision 5 Reference: CS_WI_BS005

Effective Date: 01Apr2018

Page 40 of 50

- Incidence of abnormalities prior to discharge from the study center on Day 4
- Changes in abnormalities between pre-dose on Day 1 and prior to discharge from the study center on Day 4

16.6. OTHER SAFETY ASSESSMENTS

24-hour Holter monitoring screening assessment, performed 7 to 14 days before randomization (with patients returning the next day for the removal of the Holter monitor), and on Day 3 pre-dose will be performed. The results of these assessments will be summarized by treatment group and time point of collection.

The Screening Holter report must have a minimum of 18 hours recording that is evaluable for rhythm analysis and the report must be reviewed as part of the inclusion criteria prior to randomization.

Alcohol breath test and trainings (including whole body plethysmography training and inhalation training) results will be presented in a listing only.

Document: Z:\RPL554\UYA25849\Biostatistics\Documentation\SAP\Verona RPL554-CO-204 SAP v1.0

Author: [name] Version Number: 1.0

Version Date: [18OCT2018]

Template No.: CS_TP_BS016 Revision 5 Reference: CS_WI_BS005

Effective Date: 01Apr2018

Page 41 of 50

APPENDIX 1. PROGRAMMING CONVENTIONS FOR OUTPUTS

IQVIA OUTPUT CONVENTIONS

Outputs will be presented according to the following:

TABLE AND LISTING OUTPUT CONVENTIONS

General:

- The first row in the body of the table or listing should be blank
- The left-hand column should start in column 1. No indenting or centering of the output should occur.
- Rounding should be done with the SAS function ROUND.
- Numbers in tables should be rounded, not truncated.
- Alphanumeric output should be left aligned.
- Numbers should be decimal point aligned.
- Whole numbers should be right aligned.
- Text values should be left aligned.
- The first letter of a text entry should be capitalized
- Listings of adverse events, concomitant medications, medical histories etc. should be sorted in chronological order, with earliest adverse event, medication or history coming first.
- The study drug should appear first in tables with treatments as columns
- In general, only present totals (across treatment groups) at baseline/randomization, and do not present them post randomization, unless the customer specifically requests it.
- If possible, include 100% frequencies in the table shell, so that it is clear what the denominator is for percentage calculations.
- All listing outputs should be sorted (preferably by Treatment, Site Number and Subject Number).
- Exponentiation will be expressed using a double asterisk, i.e., mm3 will be written as mm**3.
- All variables that are output in the CRF (which have data present) should appear in the listings, along with all derived data appearing in the corresponding tables
- The width of the entire output should match the linesize.

Univariate Statistics:

• Statistics should be presented in the same order across tables (i.e., n, Mean, SD, Median, Minimum, Maximum)

Document: Z:\RPL554\UYA25849\Biostatistics\Documentation\SAP\Verona RPL554-CO-204 SAP v1.0

Author: [name] Version Number: 1.0

Version Date: [18OCT2018]

Template No.: CS_TP_BS016 Revision 5 Reference: CS_WI_BS005

Effective Date: 01Apr2018

Page 43 of 50

- Table statistics should line up under the N part of the (N=XXX) in the table header. All decimal points should line up. If the minimum and maximum are output on 1 line as Minimum, Maximum then the comma should line up with the decimal point.
- If the original data has N decimal places, then the summary statistics should have the following decimal places: Minimum and maximum: N

Mean, median and CV%: N + 1

SD: N + 2

Frequencies and percentages (n and %):

• Percent values should be reported inside parentheses, with 1 space between the count and the left parenthesis of the percentage. Parentheses should be justified to accept a maximum of 100.0 as a value and padded with blank space if the percent is less than 100.0. An example is given below:

77 (100.0%) 50 (64.9%) 0 (0.0%)

Percentages will be reported to 1 decimal place, except percentages <100.0% but >99.9% will be presented as '>99.9%' (e.g., 99.99% is presented as >99.9%); and percentages < 0.1% will be presented as '<0.1%' (e.g., 0.08% is presented as <0.1%). Rounding will be applied after the <0.1% and >99.9% rule.

e.g. (<0.1%)

(6.8%)

(>99.9%)

Percentages may be reported to 0 decimal places as appropriate (for example, where the denominator is relatively small).

• Where counts are zero, percentages of 0.0% should appear in the output.

Confidence Intervals:

- As a rule, confidence intervals are output to 1 place more than the raw data, and standard deviations and standard errors to 2 places more than the raw data
- Confidence intervals should be justified so that parentheses displayed on consecutive lines of a table "line up".
- Boundary values of confidence intervals should be separated by a comma.
- Boundary values should be padded as necessary to accept negative values and to allow alignment of the decimal place.
- An example is given below:

(-0.12, -0.10)

(9.54, 12.91)

P-values:

Document: Z:\RPL554\UYA25849\Biostatistics\Documentation\SAP\Verona RPL554-CO-204 SAP v1.0

Author: [name] Version Number: 1.0

Version Date: [18OCT2018]

Template No.: CS_TP_BS016 Revision 5 Reference: CS_WI_BS005

Effective Date: 01Apr2018

Page 44 of 50

• P-values should be reported to 3 decimal places, except values <1.000 but >0.999 will be presented as '>0.999' (e.g., 0.9998 is presented as >0.999); and values <0.001 will be presented as '<0.001' (e.g., 0.0009 is presented as <0.001). Rounding will be applied after the <0.001 and >0.999 rule

Ratios:

• Ratios should be reported to 1 more decimal place than the original data.

Spacing:

• There must be a minimum of 1 blank space between columns (preferably 2)

Denominators:

- If a different count other than the population count is used for a denominator (within the table) to calculate percentages, there should be a row in the table that identifies that number "n".
- Alternatively, a footnote should be included in each table with percentages to indicate the denominator for percentages.

Missing values

- A "0" should be used to indicate a zero frequency.
- A blank will be used to indicate missing data in an end-of-text table or subject listing.

FIGURE OUTPUT CONVENTIONS

- Figures should be provided in RTF files using the SAS Output Delivery System (ODS), as Computer Graphics Metafile (CGM) formatted graphical output generated by SAS.
- The CGM file itself should contain the title or footer.
- The image should be clear and of high quality when viewed in the Word document, and when printed.
- In general, boxes around the figures should be used.

DATES & TIMES

Depending on data available, dates and times will take the form DDMMMYYY THH:MM:SS.

Document: Z:\RPL554\UYA25849\Biostatistics\Documentation\SAP\Verona RPL554-CO-204 SAP v1.0

Author: [name] Version Number: 1.0

Version Date: [18OCT2018]

Template No.: CS_TP_BS016 Revision 5 Reference: CS_WI_BS005

Effective Date: 01Apr2018

Page 45 of 50

SPELLING FORMAT

English US.

PRESENTATION OF TREATMENT GROUPS

For outputs, treatment groups will be represented as follows and in that order:

Treatment Group	For Tables, Graphs and Listings
Tiotropium/olodaterol 5 μg /5 μg once daily +	RPL554 1.5 mg
RPL554 1.5 mg	RFL334 1.3 mg
Tiotropium/olodaterol 5 μg /5 μg once daily + RPL554 6.0 mg	RPL554 6.0 mg
Tiotropium/olodaterol 5 μg /5 μg once daily +	Placebo
Placebo twice daily	
Non-randomized (where applicable)	Non-randomized

PRESENTATION OF TREATMENT SEQUENCES

For outputs, treatment sequences will be represented as follows and in that order:

Treatment Group	For Tables, Graphs and Listings
RPL544 1.5 mg / RPL544 6.0 mg / Placebo	Seq 1
RPL544 1.5 mg / Placebo / RPL544 6.0 mg	Seq 2
RPL544 6.0 mg / RPL544 1.5 mg / Placebo	Seq 3
RPL544 6.0 mg / Placebo / RPL544 1.5 mg	Seq 4
Placebo / RPL544 1.5 mg / RPL544 6.0 mg	Seq 5
Placebo / RPL544 6.0 mg / RPL544 1.5 mg	Seq 6
Non-randomized (where applicable)	Non-randomized

Document: Z:\RPL554\UYA25849\Biostatistics\Documentation\SAP\Verona RPL554-CO-204 SAP v1.0

Author: [name] Version Number: 1.0

Version Date: [18OCT2018]

Template No.: CS_TP_BS016 Revision 5 Reference: CS_WI_BS005

Effective Date: 01Apr2018

PRESENTATION OF VISITS

For outputs, visits will be represented as follows and in that order, considering there will be 3 treatment periods (1 to 3):

Long Name (default)	Short Name
Screening	Scr
Day 1	Day 1
Day 2	Day 2
Day 3	Day 3
End of Study	EOS
Overall (where applicable)	Overall

LISTINGS

All listings will be ordered by the following (unless otherwise indicated in the template):

- Randomized treatment group (or treatment received if it's a safety output), first by active dose [by ascending dose group] and then placebo.
- Center-patient ID,
- Date (where applicable),
- For listings where non-randomized patients are included, these will appear in a category after the randomized treatment groups labeled 'Non-randomized'.

APPENDIX 2. Partial Date Conventions

Imputed dates will NOT be presented in the listings.

Document: Z:\RPL554\UYA25849\Biostatistics\Documentation\SAP\Verona RPL554-CO-204 SAP v1.0

Author: [name] Version Number: 1.0

Version Date: [18OCT2018]

Template No.: CS_TP_BS016 Revision 5 Reference: CS_WI_BS005

Effective Date: 01Apr2018

ALGORITHM FOR TREATMENT EMERGENCE OF ADVERSE EVENTS

START DATE	STOP DATE	ACTION
Known	Known	If start date < study med start date, then not TEAE
		If start date >= study med start date, then TEAE
	Partial	If start date < study med start date, then not TEAE
		If start date >= study med start date, then TEAE
	Missing	If start date < study med start date, then not TEAE
		If start date >= study med start date, then TEAE
Partial, but known	Known	Not TEAE
components show that it		
cannot be on or after study		
med start date		
	Partial	Not TEAE
	Missing	Not TEAE
Partial, could be on or after	Known	If stop date < study med start date, then not TEAE
study med start date		If stop date >= study med start date, then TEAE
	Partial	Impute stop date as latest possible date (i.e. last day of month
		if day unknown or 31st December if day and month are
		unknown), then:
		If stop date < study med start date, then not TEAE
		If stop date >= study med start date, then TEAE
	Missing	Assumed TEAE
Missing	Known	If stop date < study med start date, then not TEAE

Document: Z:\RPL554\UYA25849\Biostatistics\Documentation\SAP\Verona RPL554-CO-204 SAP v1.0

Author: [name] Version Number: 1.0

Version Date: [18OCT2018]

Template No.: CS_TP_BS016 Revision 5 Reference: CS_WI_BS005

Effective Date: 01Apr2018

Page 48 of 50

START DATE	STOP DATE	ACTION
		If stop date >= study med start date, then TEAE
	Partial	Impute stop date as latest possible date (i.e. last day of month
		if day unknown or 31st December if day and month are
		unknown), then:
		If stop date < study med start date, then not TEAE
		If stop date >= study med start date, then TEAE
	Missing	Assumed TEAE

ALGORITHM FOR PRIOR / CONCOMITANT MEDICATIONS

START DATE	STOP DATE	ACTION	
Known	Known	If stop date < study med start date, assign as prior	
		If stop date >= study med start date and start date <= end of treatment,	
		assign as concomitant	
		If stop date >= study med start date and start date > end of treatment, assign	
		as post study	
	Partial	Impute stop date as latest possible date (i.e. last day of month if day	
		unknown or 31st December if day and month are unknown), then:	
		If stop date < study med start date, assign as prior	
		If stop date >= study med start date and start date <= end of treatment,	
		assign as concomitant	
		If stop date >= study med start date and start date > end of treatment, assign	
		as post treatment	
	Missing	If stop date is missing could never be assumed a prior medication	
		If start date <= end of treatment, assign as concomitant	
		If start date > end of treatment, assign as post treatment	

Document: Z:\RPL554\UYA25849\Biostatistics\Documentation\SAP\Verona RPL554-CO-204 SAP v1.0

Author: [name] Version Number: 1.0

Version Date: [180CT2018]

Template No.: CS_TP_BS016 Revision 5 Reference: CS_WI_BS005

Effective Date: 01Apr2018

Page 49 of 50

START DATE	STOP DATE	ACTION
Partial	Known	Impute start date as earliest possible date (i.e. first day of month if day unknown or 1st January if day and month are unknown), then: If stop date < study med start date, assign as prior
		If stop date >= study med start date and start date <= end of treatment, assign as concomitant
		If stop date >= study med start date and start date > end of treatment, assign as post treatment
	Partial	Impute start date as earliest possible date (i.e. first day of month if day unknown or 1st January if day and month are unknown) and impute stop
		date as latest possible date (i.e. last day of month if day unknown or 31st December if day and month are unknown), then:
		If stop date < study med start date, assign as prior If stop date >= study med start date and start date <= end of treatment, assign as concomitant
		If stop date >= study med start date and start date > end of treatment, assign as post treatment
	Missing	Impute start date as earliest possible date (i.e. first day of month if day unknown or 1st January if day and month are unknown), then: If stop date is missing could never be assumed a prior medication If start date <= end of treatment, assign as concomitant If start date > end of treatment, assign as post treatment
Missing	Known	If stop date < study med start date, assign as prior If stop date >= study med start date, assign as concomitant Cannot be assigned as 'post treatment'

Document: Z:\ RPL554\UYA25849\Biostatistics\Documentation\SAP\Verona RPL554-CO-204 SAP v1.0

Author: [name] Version Number: 1.0

Version Date: [18OCT2018]

Template No.: CS_TP_BS016 Revision 5 Reference: CS_WI_BS005

Effective Date: 01Apr2018

Page 50 of 50

START DATE	STOP DATE	ACTION
	Partial	Impute stop date as latest possible date (i.e. last day of month if day
		unknown or 31st December if day and month are unknown), then:
		If stop date < study med start date, assign as prior
		If stop date >= study med start date, assign as concomitant
		Cannot be assigned as 'post treatment'
	Missing	Assign as concomitant

Document: Z:\ RPL554\UYA25849\Biostatistics\Documentation\SAP\Verona RPL554-CO-204 SAP v1.0

Author: [name] Version Number: 1.0

Version Date: [18OCT2018]

Template No.: CS_TP_BS016 Revision 5 Reference: CS_WI_BS005

Effective Date: 01Apr2018

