1.2 Summary of Risks and Benefits

Data from non-clinical studies suggested a potential for hypotension and tachycardia. However, in the clinical studies to date RPL554 has been well tolerated in moderate to severe COPD patients, healthy subjects, asthmatics and allergic rhinitics. The most common adverse events that have been reported at least twice in subjects who have received single or multiple doses of the nebulized suspension of RPL554 were generally mild and in descending order of frequency are headache, cough, dizziness, and palpitations. Adverse events for single and multiple dose studies are summarized in Investigator's Brochure Section 6.3.

The suspension formulation of RPL554 is pH balanced, and has favorable non-clinical toxicology and pharmacokinetic data.

There has been no evidence of significant adverse events related to the cardiovascular or gastrointestinal systems, except associated with an increase in heart rate at high doses (12 mg to 24 mg). These small increases in heart rate may relate to the PDE3 inhibitory activity of the compound. In single dose studies there appears to be an increase in the rate of headache, which is most pronounced at doses over 6 mg. There was no other apparent dose related adverse events, with the exception of palpitations in patients dosed at 24 mg. In particular, Holter findings have indicated no arrhythmogenic potential in the completed studies. Results from multiple dose data in patients with COPD suggests a transient increase in dizziness, the majority of which occurred during spirometry or dosing; otherwise, the rate of adverse events was similar in RPL554 and placebo treated patients. There was an apparent increase in mild adverse events in healthy subjects treated with high doses of RPL554, which may be associated with the higher serum levels in healthy subjects than in those with obstructive lung disease.

As RPL554 is planned in this study to be administered for only 6 days (12 doses) over two treatment periods (placebo is administered in the third treatment period), any benefit to the patients will be restricted to the immediate short-term.

Verona Pharma plc CONFIDENTIAL Page 16 of 66

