6.3.1.1 Pre-Dose Assessments

The following assessments will be performed prior to dosing:

- Confirm that respiratory medications were withheld as required
- Questioning for adverse events
- Urine pregnancy test (females of childbearing potential only)
- 12-lead ECG
- Dyspnea scale
- Vital signs
- Brief physical examination (see Section 7.4.5)
- Spirometry; 1 hour (±5 minutes) and immediately prior to study treatment administration
- Whole body plethysmography
- Inhalation training

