7.4.1.2 Recording and Assessing Adverse Events

All adverse events, whether reported spontaneously by the patient, in response to open questioning on treatment days or observed by the Investigator or his/her staff, will be recorded from informed consent until the end of study visit. The start and stop time will be recorded and adverse events will be assessed by the Investigator for the following:

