6.3. REPEAT/RESCHEDULE, UNSCHEDULED VISITS AND EARLY TERMINATION DATA

In general, for by-visit summaries, data recorded at the nominal visit will be presented. If a visit is repeated/rescheduled due to variability in FEV₁ or other reason, the repeated/rescheduled visit, will be listed and summarized as the valid visit (same visit number assigned), at the discretion of the Investigator. Unscheduled measurements will not be included in by-visit summaries, but will contribute to the endpoint value, at the discretion of the Investigator. For example, if an unscheduled visit occurred at 10 hours post-dose on Day 3, then this value will be considered in the calculation of the average FEV₁ over 12 hours (AUC_{0-12h} FEV₁) on Day 3. Any unscheduled or unplanned readings will be presented within the patient listings.

Early termination data will be mapped according to the visit number the termination occurred for by-visit summaries. If early termination occurs pre-first dose (after baseline), then it is summarized at the actual visit. If

Document: Z:\RPL554\UYA25849\Biostatistics\Documentation\SAP\Verona RPL554-CO-204 SAP v1.0

Author: [name] Version Number: 1.0

Version Date: [18OCT2018]

Template No.: CS_TP_BS016 Revision 5 Reference: CS_WI_BS005

Effective Date: 01Apr2018

Page 17 of 50

termination is after first dose in period or during the following wash-out period, data collected remains at the visit performed. However, if the patient returns for end of study, then this data will be mapped to end of study visit.

If AE data occurs in the 7 to 14-day gap between treatment periods, these will be mapped to the earlier of the two treatment periods. Similarly, the AE will be mapped to the last treatment group received. If AE data occurs in the post-treatment period, these will be mapped to the last treatment period and last treatment group received.

Listings will include scheduled, unscheduled, repeat/reschedule and early discontinuation data.

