16.1. ADVERSE EVENTS

Adverse Events (AEs) will be coded by MedDRA dictionary using the version specified in the data management plan.

Treatment emergent adverse events (TEAEs) are defined as AEs that started or worsened in severity on or after the first dose of study medication, based on the investigator assessment of severity. TEAEs will be assigned to treatment groups based on actual treatment received. TEAEs, like medications, may be assigned to multiple treatment groups due to the cross-over design of the study. This will depend on the occurrence date and duration of each TEAE.

See Appendix 2 for handling of partial dates for AEs. In the case where it is not possible to define an AE as treatment emergent or not, the AE will be classified by the worst case; i.e. treatment emergent.

Document: Z:\RPL554\UYA25849\Biostatistics\Documentation\SAP\Verona RPL554-CO-204 SAP v1.0

Author: [name] Version Number: 1.0

Version Date: [18OCT2018]

Template No.: CS_TP_BS016 Revision 5 Reference: CS_WI_BS005

Effective Date: 01Apr2018

Page 36 of 50

An overall summary of number of patients within each of the categories described in the sub-section below, will be provided as specified in the templates.

Listings will include TEAEs and Non-TEAEs.

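### SAP Appendix 2 decides treatment emergence by calendar date, against the first-dose definition in SAP 16.1, so a pre-dose event on Day 1 of Period 1 counts as treatment emergent

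*SAP*

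**What the plan says.** **Emergence.** SAP 16.1 defines TEAEs as "AEs that started or worsened in severity on or after the first dose of study medication". The algorithm in SAP Appendix 2 compares dates only. For every row with a known start date, whatever is known of the stop date, the rule is: "If start date >= study med start date, then TEAE". SAP 6.1 likewise defines the reference start as a day, not a date and time.

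**What is recorded.** Protocol 7.4.1.2 says of adverse events: "The start and stop time will be recorded". Protocol 5.11 requires the exact date and time of each administration in the eCRF, and 5.4.2.1 requires the start and end times of nebulization.

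**Treatment assignment.** SAP 16.1 says a TEAE may belong to more than one treatment group, and adds: "This will depend on the occurrence date and duration of each TEAE". SAP 6.3 says: "If AE data occurs in the 7 to 14-day gap between treatment periods, these will be mapped to the earlier of the two treatment periods". It then assigns those events to the treatment group most recently received.

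**Before the Day 1 dose.** Protocol 6.3.1.1 lists questioning for adverse events, plethysmography, and "Spirometry; 1 hour (±5 minutes) and immediately prior to study treatment administration". Protocol 5.4.2 puts the first dose between 7 and 11 am.

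**The concern.** The table in Appendix 2 is what a programmer will code. As written, it labels an event as treatment emergent when the recorded times show that it began before any study treatment.

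Such events are foreseeable. Patients come to the Day 1 morning having withheld short-acting bronchodilators for 8 hours, and they perform spirometry twice before dosing. Protocol 1.2 reports from multiple-dose data in COPD a "transient increase in dizziness, the majority of which occurred during spirometry or dosing". Dizziness at the pre-dose spirometry of Period 1 cannot be due to RPL554, yet it would appear in the TEAE tables under whichever treatment the patient was about to receive.

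In a crossover, the by-treatment safety tables depend on the attribution rule. Two programmers, one following the text of 16.1 and one following Appendix 2, could produce different TEAE tables from the same data. In Periods 2 and 3 they could also place the same event under different treatments.

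**Working it through.** The documents state no figure on this point that could be reproduced. The check is to apply both rules to the same events and then measure the window in which they differ.

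**Step 1. Apply both rules on Day 1 of Period 1.** Take a first dose at 09:00 and a new event that does not later worsen.

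| Event onset | Appendix 2 (date) | SAP 16.1 (first dose) |
|---|---|---|
| 23:30 the day before | not TEAE | not TEAE |
| 00:30 on Day 1 | TEAE | not TEAE |
| 08:00 on Day 1 | TEAE | not TEAE |
| 09:05 on Day 1 | TEAE | TEAE |

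Doses at 07:00 and 11:00 give the same pattern. The rules differ only between midnight and the dose.

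**Step 2. Size of the window.** With dosing between 07:00 and 11:00 it is 7 to 11 hours, or 7/24 = 29% to 11/24 = 46% of the dosing date. It occurs once per patient. With about 70 patients that is about 70 mornings, or about 70/3 = 23 per treatment, because the six sequences are allocated equally.

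**Step 3. Periods 2 and 3.** These supply about 2 × 70 = 140 further Day 1 mornings. The patient has already had a first dose of study medication, so a new pre-dose event is a TEAE under both rules. Only its attribution is open:

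- SAP 16.1 goes by occurrence date, which is the date of the new period and so suggests the new treatment.
- SAP 6.3 assigns events in the gap to the treatment last received, which suggests the previous one. The protocol counts the gap from the last dose, so the pre-dose morning can be read as part of it.

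Neither section mentions the pre-dose morning.

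**Step 4. Scale under an assumption.** Suppose background events occur at a constant hourly rate. SAP 6.3 charges washout events to the preceding treatment. The Period 1 treatment therefore collects events for 60 hours (first dose to last dose, Day 1 morning to Day 3 evening) plus 7 to 14 days (168 to 336 hours), which is 228 to 396 hours. The share of the Period 1 count that falls before the dose is then:

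- lowest: 7/(7 + 396) = 1.7%
- highest: 11/(11 + 228) = 4.6%

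This shows scale only. The documents give no event rate for the window, and a constant rate ignores both the pre-dose procedures and the quieter hours of the night.

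**The case against.** The best defence is that SAP 16.1 already has the right definition. It refers to Appendix 2 for partial dates, and the appendix is titled accordingly. On that view the text governs and the table is a convention for incomplete data. This stands in part: the defect is an inconsistency inside the SAP, not a considered decision to classify by calendar date. It does not remove the defect, because the first rows of the table cover fully known start dates. SAP 16.1 also reserves its worst-case rule for events whose status cannot be determined, and here the recorded times determine it.

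The consequences are also limited. The investigator judges causality with time course in mind (Protocol 14.3), TEAEs are tabulated by relationship, and listings show both TEAEs and other events. SAP 16 plans no statistical comparison of treatments on safety data unless specified. All of this stands and keeps the point small.

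A reader might go further in two ways that the documents do not support.

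- **That every treatment's event rate is inflated in every period.** Events can be added only in Period 1. In Periods 2 and 3 they are TEAEs either way and at most move from one treatment to another. Even that is an ambiguity, since SAP 6.3 can be read to give the right answer.
- **That 9% to 13% of events are misclassified,** by setting 7 to 11 hours against a 72-hour stay: 7/79 = 8.9% and 11/83 = 13.3%. Any diluted risk ratio built on those figures fails with them. SAP 6.3 adds the washout to the denominator, and patients arrive on the morning of Day 1, so most of the hours since midnight are not spent in the clinic.

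**Conclusion.** The point holds in a narrow form. The known-start-date rows of Appendix 2 contradict SAP 16.1 and, coded as written, give a wrong result for events on Day 1 of Period 1 that begin before the first dose. For Periods 2 and 3 the SAP is ambiguous about attribution, not demonstrably wrong.

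The number of affected events cannot be calculated from the documents. It is probably small: a window of 7 to 11 hours on about 70 mornings, and under a constant rate a low single-digit percentage of the Period 1 count. Equal allocation to sequences spreads the added Period 1 events about evenly over the three treatments in expectation. Efficacy is untouched.

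The conclusion assumes that the onset times required by Protocol 7.4.1.2 reach the analysis database, and that the algorithm is programmed as printed. It deserves correction because the SAP should yield one TEAE table, and because dizziness during spirometry is a finding that the protocol itself names.

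**What to change.** 1. **Appendix 2, known-start-date rows.** Where the onset time is known, compare the event's start date and time with the date and time of the first dose in Period 1. Onset before that dose is not a TEAE unless the event later worsens, as 16.1 already provides. Keep the date-only worst-case rule for events with a missing time.
2. **SAP 16.1 and 6.3.** State that an event starting before the first dose of Period 2 or 3 is assigned to the preceding period and treatment. Make the occurrence-date wording in 16.1 refer to date and time.
3. **Dose time.** Define it as the start of the first administration in the period. Protocol 5.4.2.1 sets Time 0 for scheduling at the end of nebulization. Using that time would push events during dosing into the pre-dose class.

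The cost is SAP wording and programming, with no new data, visits or patients. The change should be made before database lock and unblinding.
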